# 4. STUDY POPULATION

### 4.1. Inclusion Criteria

Subjects must meet ALL of the following inclusion criteria to be eligible for enrollment into the study:

- 1. Raynaud's phenomenon (defined as a history of digital cold sensitivity associated with color changes of cyanosis and pallor, with on average at least 5 attacks per week during the winter period) secondary to SSc based on either:
  - a. Diagnosis of SSc (using the American College of Rheumatology/European League Against Rheumatism [ACR/EULAR 2013] and/or LeRoy and Medsger classification) (LeRoy 2001, van den Hoogen 2013)
  - b. Diagnosis of very early SSc (using the Very Early Diagnosis of Systemic Sclerosis [VEDOSS] criteria) (Avouac 2011)
- 2. 18 to 75 years of age, inclusive
- 3. Females must meet a and c or b and males must meet d to qualify for the study:
  - a. Female and not pregnant or breastfeeding
  - b. Female and not of child-bearing potential by one of the following:
    - Postmenopausal, defined as no menses for 12 months without an alternative medical cause
    - Permanent sterilization procedure, such as hysterectomy, bilateral salpingectomy, or bilateral oophorectomy
  - c. Female of child-bearing potential and using a highly effective contraception method during treatment and for 30 days following treatment that can achieve a failure rate of less than 1% per year when used consistently and correctly. The following methods are considered highly effective birth control methods:
    - Combined (estrogen and progestogen containing) hormonal contraception associated with inhibition of ovulation, which may be oral, intravaginal, or transdermal
    - Progestogen-only hormonal contraception associated with inhibition of ovulation, which may be oral, injected, or implanted
    - Intrauterine device (IUD)
    - Intrauterine hormone-releasing system (IUS)
    - Bilateral tubal occlusion
    - Vasectomized partner
    - Sexual abstinence (complete sexual abstinence defined as refraining from heterosexual intercourse for the entire period of risk associated with study treatments). The reliability of sexual abstinence needs to be evaluated in relation to the duration of the clinical study and the preferred and usual

lifestyle of the subject. Periodic abstinence (calendar, symptothermal, post-ovulation methods), withdrawal (coitus interruptus), spermicides only, and lactational amenorrhoea method (LAM) are not acceptable methods of contraception.

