#### 10.2.8. Pregnancy Testing

A serum pregnancy test for beta-human chorionic gonadotropin ( $\beta$ -hCG) will be performed on WOCBP at screening to determine eligibility and at each Treatment Visit. At each treatment visit, urine pregnancy tests ( $\beta$ -hCG) will be performed, and a negative result is required to be documented, prior to administration of study treatment. The results of the serum pregnancy test

at each Treatment Visit are not required prior to dosing. If at any point there is a case of a positive urine  $\beta$ -hCG test, the subject will have study treatment interrupted. If the serum test confirms positive, the subject will be discontinued from the study treatment and all the necessary follow up will be conducted as per Section 10.8.6. If the serum test is negative, the subject may resume study treatment.

At Treatment Visit 1, WOCBP will also be provided with a urine pregnancy test that is to be taken at home prior to the subject's Follow-Up visit on the same day of the Follow-Up visit. During the first Treatment Visit subjects will receive adequate training on the use of the home pregnancy test and will be informed on how to properly communicate the results of their test. If the result of the home pregnancy test is positive, subjects will be required to undergo a serum pregnancy test. If the serum test confirms positive, all necessary follow-up will be conducted as per Section 10.8.6. If the serum test is negative, no further follow-up is required.

Women who are surgically sterile or who are postmenopausal are not considered to be of child-bearing potential. Postmenopausal is defined as 12 consecutive months with no menses without an alternative medical cause.

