## Table 2:Clinical Laboratory Tests

Pregnancy Testing a	Coagulation	Virology Screening				
Serum pregnancy test beta-human chorionic gonadotropin (β-hCG)	Activated partial thromboplastin time (PTT)	e Hepatitis C virus				
Urine β-hCG	Fibrinogen					
	International Normalized Ratio (INR)	)				
	Prothrombin time (PT)					
	Thrombin time (TT)					
Urinalysis	Hematology					
Appearance	Hematocrit					
Bilirubin	Hemoglobin					
Color	Mean corpuscular hemoglobin (MCH	I)				
Glucose	Mean corpuscular hemoglobin concer	ntration (MCHC)				
Ketones	Mean corpuscular volume (MCV)					
Leukocyte esterase	Platelet count					
Microscopic examination of sediment	Red blood cell (RBC) count					
Nitrite	White blood cell (WBC) count with differential					
Occult blood						
рН						
Protein						
Specific gravity						
Urobilinogen						
Serum Chemistry		Endocrinology				
Alanine aminotransferase (ALT)	Phosphorus	Thyroid-stimulating hormone				
Albumin	Potassium	(TSH)				
Alkaline phosphatase (ALP)	bouldin	hyroxine (T4) free				
Aspartate aminotransferase (AST)	Total bilirubin	Triiodothyronine (T3) free				
Bicarbonate	Total cholesterol					
Blood urea nitrogen (BUN)	Total protein					
Calcium	Triglycerides					
Chloride	Uric acid					
Creatinine						
Direct bilirubin						
Creatine kinase (CK)						
Glucose						
Lactate dehydrogenase (LDH)						

Biomarkers
Endothelin-1
Factor VIII activity
Intracellular adhesion molecule 1 [ICAM-1]
Plasminogen activator inhibitor-1 [PAI-1] activity
PAI-1 antigen
Serotonin
Tissue-type plasminogen activator antigen [t-PA]
Vascular adhesion molecule 1 (VCAM-1)
Vascular endothelial growth factor (VEGF)
Von Willebrand factor [VWF]
Urine Drug Screen
Amphetamines, barbiturates, benzodiazepines, cocaine, marijuana, methadone, methamphetamine,

methylenedioxymethamphetamine, opiate, oxycodone, phencyclidine

a Required only for women of child-bearing potential.

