c The Screening Period will last for up to 28 days prior to Treatment Visit 1 (Day -28 to 1).

d Predose assessments are to occur on each Treatment Visit at approximately the same time of the day after the subject has acclimatized for at least 20 minutes in a temperature-controlled room (23 [± 1]°C).

- e Postdose assessments are to occur at each Treatment Visit at 45 (± 5) minutes after study treatment administration and re-acclimatization for at least 20 minutes in a temperature-controlled room (23 [± 1]°C).
- f Subjects are required to undergo acclimatization for at least 20 minutes in a temperature-controlled room (23 [± 1]°C) and IR thermography is used to assess digit temperature to determine eligibility.

g A full physical examination is performed per the site's standard of care at Screening. A symptom-based physical exam is performed at the end of final Treatment Visit (Treatment Visit 3).

h An exam of the hands for digital ulcers is performed at each Treatment Visit at Check-in.

i Postdose PK and biomarkers blood samples will be collected after the post-cold challenge digital blood flow assessment are completed. Refer to Section 10.5 for further information on blood sample collection.

j Pregnancy tests are required for all women of child-bearing potential. A serum pregnancy test is performed at Screening to determine eligibility and at each Treatment Visit. Urine pregnancy tests with a negative result are required prior to dosing at each Treatment Visit. Results of the serum pregnancy test at each Treatment Visit are not required prior to dosing. A home pregnancy test will be performed as part of the Follow-Up Visit.

k Urine drug screen at Screening is performed to determine eligibility. The results of subsequent urine drug screens are not required prior to initiating study conduct of each Treatment Visit. However, if at any time a subject test positive for any drug included in the urine drug screen, the subject may be discontinued from study treatment at the discretion of the Sponsor.

 The first day of the most recent menstrual cycle is documented at each Treatment Visit at Check-in.

[figure not shown]
m Subjects will be asked about their adherence to restrictions described in Section 5. Responses will be documented in the eCRF.

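### Inclusion criterion 3 combines its female conditions without brackets, and its natural reading lets a permanently sterilized woman who is breastfeeding qualify without meeting condition a

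*Combined protocol and SAP*

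**What the plan says.** Section 4.1 opens with "Subjects must meet ALL of the following inclusion criteria to be eligible for enrollment into the study". Criterion 3 then has four lettered conditions, joined by this sentence, which is worded identically in the synopsis: "Females must meet a and c or b and males must meet d to qualify for the study".

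The conditions for females are:

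- **a:** "Female and not pregnant or breastfeeding".
- **b:** not of child-bearing potential. One route is menopause, meaning 12 months without menses and no other medical explanation. The other is "Permanent sterilization procedure, such as hysterectomy, bilateral salpingectomy, or bilateral oophorectomy".
- **c:** the route for women who could become pregnant, which reads "Female of child-bearing potential and using a highly effective contraception method during treatment and for 30 days following treatment". Bilateral tubal occlusion is listed here, among the accepted contraceptive methods.

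Condition d concerns males only.

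Section 10.2.8 adds: "Women who are surgically sterile or who are postmenopausal are not considered to be of child-bearing potential". On testing, the Appendix 1 footnote reads "Pregnancy tests are required for all women of child-bearing potential", and the Table 2 footnote reads "Required only for women of child-bearing potential".

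**The concern.** The sentence mixes *and* with *or* and does not say which binds first. If *and* binds first, as is usual, meeting b alone is enough and condition a applies only to women who enter through c.

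The pregnancy half of a is largely moot for a woman who meets b. The breastfeeding half is not, because permanent sterilization does not make breastfeeding impossible. Condition a shows that the sponsor treats breastfeeding as a reason not to enrol, and nothing in the documents says that sterilized women are to be handled differently.

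At stake is a small safety matter, and an eligibility rule that sites in a multicenter study could apply in opposite ways.

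**Working it through.** The plan states no figure on this point and no sample-size arithmetic applies. The check is one of logic, followed by a search for other text that would close the gap.

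**Step 1: compare the two readings.** Conditions b and c cannot both hold, since one requires that a woman is not of child-bearing potential and the other that she is. That leaves six profiles.

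| Meets a | Meets b | Meets c | (a and c) or b | a and (b or c) |
|---|---|---|---|---|
| yes | yes | no | eligible | eligible |
| yes | no | yes | eligible | eligible |
| yes | no | no | not eligible | not eligible |
| **no** | **yes** | **no** | **eligible** | **not eligible** |
| no | no | yes | not eligible | not eligible |
| no | no | no | not eligible | not eligible |

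The readings differ in one row of six: b met, a not met.

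**Step 2: choose the more natural reading.** Besides the usual precedence of *and*, the order of the letters points to (a and c) or b. The sentence skips b, pairs a with c, and leaves b standing alone. A drafter who wanted a for every woman would more naturally have written the letters in sequence. This is an inference from the wording and does not settle what was meant.

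**Step 3: identify who is in that row.**

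- *Menopause route.* It requires that no other medical cause explains the absence of menses, so amenorrhoea due to lactation should not qualify.
- *Tubal occlusion.* It sits under c, so these women must meet a on either reading.
- *Permanent sterilization route.* The text of b does not mention breastfeeding, and Section 10.2.8 confirms that surgically sterile women are not of child-bearing potential. This is the route that stays open.

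**Step 4: look for another barrier.**

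- None of the 39 exclusion criteria in Section 4.2 names breastfeeding or lactation.
- Exclusion 24 covers major surgery within 6 months before Screening. It may remove a woman sterilized recently. It does not reach one still breastfeeding more than 6 months after the procedure, or one whose procedure is not judged major; the term is not defined.
- Exclusion 26 gives the investigator discretion over disorders and treated malignancy. Breastfeeding is neither.
- The remark on the lactational amenorrhoea method concerns acceptable contraception and belongs to c.
- Pregnancy tests are required for women of child-bearing potential, and they do not detect breastfeeding.
- Section 10.2.2 records reproductive status and Section 10.8.2 records menstrual dates. Neither sets an enrolment rule.

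**Step 5: count the active doses.** Sections 3 and 6.3 give each subject three single doses. In each stage one of the three treatments is placebo, so 3 − 1 = 2 are temanogrel.

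**The case against.** The strongest reply is that the sentence is ambiguous, and that condition a itself suggests the sponsor wanted it to apply to all women. On a and (b or c) there is no gap. That stands as a possible reading, so it would be too strong to say that the protocol plainly admits breastfeeding women. The documents support less: the natural reading admits this one profile, and the wording does not exclude that reading.

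The second reply is Exclusion 24. A hysterectomy around delivery would ordinarily count as major surgery, and a salpingectomy or oophorectomy may. Many recent cases are therefore probably excluded already. This narrows the group but does not empty it.

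The third is that pregnancy is handled elsewhere, through testing (Section 10.2.8) and withdrawal from study treatment after a positive test (Section 10.8.6). That is right, and the point here is confined to breastfeeding.

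A reader might also infer three things that the documents do not support:

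- That an infant could be exposed through three active doses. At most two are active, and the documents give no data on transfer into milk.
- That the incomplete embryo-fetal studies in Section 3.2.2 bear on this. They are discussed there for including women of child-bearing potential, which is a pregnancy question. Condition a is the better evidence of intent on breastfeeding.
- That the number affected can be worked out from the planned enrolment. The ratio of women to men in Section 3.2.2 says nothing about how many women are both breastfeeding and permanently sterilized.

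**Conclusion.** The point holds as a minor defect in an operative rule. Criterion 3 allows two readings with opposite results for one profile, and the more natural one lets a breastfeeding woman qualify through permanent sterilization without meeting condition a. No other provision fully closes this.

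The group is expected to be very rare. That is a judgement, because the documents give no rate. The conclusion rests on the usual precedence of *and* over *or*, and on major surgery in Exclusion 24 being read so that it does not cover every sterilization procedure still relevant at Screening. Power, type I error and the analysis sets are unaffected.

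The Note to File (Amendment 1) records that enrolment was terminated after the decision of 25 August 2022. The remaining practical value lies in the protocol text and in any later protocol that reuses it.

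**What to change.** In both the synopsis and Section 4.1, rewrite the lead sentence of criterion 3 so that the protocol's own condition a applies to every female, for example: *Females must meet a, and either b or c; males must meet d.* The lettered conditions can stay as they are.

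The cost is one sentence in two places. Compared with the natural reading, eligibility changes for the single profile that meets b but not a; every other profile is unchanged. Any loss to recruitment is limited to women whom condition a, applied to all females, would keep out.

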# 4.2. Exclusion Criteria

Subjects who meet ANY of the following exclusion criteria will not be eligible for enrollment into the study:

- 1. Active digital ulcer(s), recent history (within 3 months of Screening) of digital ulcers, or history of recurrent digital ulcerations that in the opinion of the Investigator increase the likelihood of developing a digital ulcer during the course of the study. Any history of gangrene, amputations, or other critical digital ischemic event.
- 2. Presence of severe contractures (advanced fixed flexion) of the digits, which in the opinion of the Investigator could prevent accurate assessment of digital perfusion of the dorsal fingers
- 3. Raynaud's phenomenon due to any cause other than SSc (eg, peripheral or central vasculopathy other than SSc, past exposure to vasculopathic agents, past frostbite injury)
- 4. Severe gastrointestinal complications related to SSc that in the opinion of the Investigator could significantly affect study drug absorption
- 5. History of gastrointestinal bleeding or active gastric or duodenal ulcers
- 6. Subject's digits do not reach a temperature of ≥ 27°C after 20 minutes of acclimatization at room temperature (23 [± 1]°C) at Screening
- 7. Any change in dosage of the following medications within 30 days of Day 1 or planned change in dosage during study participation: Calcium channel blockers (CCBs), phosphodiesterase type 5 inhibitors (PDE5i), alpha-blockers, or angiotensin II receptor blockers (ARBs).
- 8. Use of nitrates within 30 days of Day 1
- 9. Use of endothelin-1 receptor antagonists (ERAs) and therapies targeting the prostacyclin receptor within 3 months of Day 1
- 10. Local treatment (of digits) with botulinum toxin within 30 days of Day 1
- 11. Surgical sympathectomy of digit within 3 months of Day 1
- 12. Use of vasoconstrictive drugs (eg, ergot derivatives, triptans) within 7 days of Day 1
- 13. Use of antiplatelet therapy with the exception of aspirin (eg, adenosine diphosphate receptor [P2Y12] inhibitors, glycoprotein IIb/IIIa inhibitors), or anti-coagulants (eg,

warfarin or direct oral anti-coagulants [DOACs], including oral thrombin inhibitors) within 7 days of Day 1

- 14. Use of any medications affecting the serotonin system (eg, selective serotonin reuptake inhibitors [SSRI], serotonin and norepinephrine reuptake inhibitors [SNRIs], atypical [second generation] antipsychotics possessing 5-HT2A pharmacology, or any other serotonergic agents possessing 5-HT2A pharmacology [eg, naftidrofuryl and the triazolopyridine antidepressant trazodone]) within 14 days of Day 1
- 15. Use of prescription medications/products or herbal preparations that are strong inhibitors or inducers of cytochrome P450 (CYP)3A4 or are strong inhibitors of P-glycoprotein within 14 days of Day 1 or 5 half-lives of the medication/product, whichever is longer. See Section 5.4 Restricted Medications for details.
- 16. Use of prescription medications/products that are strong inhibitors of multidrug and toxin extrusion transporter-1 (MATE1) or organic cation transporter-2 (OCT2) within 14 days of Day 1 or 5 half-lives of the medication/product, whichever is longer. See Section 5.4 Restricted Medications for details.
- 17. Use of prescription medications/products that are sensitive or moderately sensitive substrates of CYP2C8 within 14 days of Day 1 or 5 half-lives of the medication/product, whichever is longer. See Section 5.4 Restricted Medications for details.
- 18. Use of prescription medications/products that are sensitive substrates of CYP3A4/5 within 14 days of Day 1 or 5 half-lives of the medication/product, whichever is longer. Exceptions are PDE5i (allowed per Exclusion Criterion #7) and atorvastatin. See Section 5.4 Restricted Medications for details.
- 19. Consumption of grapefruit or grapefruit juice within 3 days of Check-in
- 20. Diabetes mellitus diagnosed more than 5 years ago or with known history of end-organ damage (diabetic retinopathy, nephropathy, neuropathy)
- 21. History of advanced heart failure (New York Heart Association [NYHA] Class 3 or 4) or myocardial infarction within 1 month prior to Screening.
- 22. Any history of stroke, seizure disorder, intracranial bleeding, or intracranial aneurysm; significant head injury requiring hospital assessment within 30 days prior to Screening
- 23. Transient ischemic attack within the 6 months prior to Screening
- 24. History of major trauma, major surgery, and/or clinically significant hemorrhage within the 6 months prior to Screening
- 25. Active hepatitis C
- 26. At the discretion of the Investigator, any history or clinical manifestation of any endocrine, allergic, dermatological, hepatic, renal, hematological, pulmonary, gastrointestinal, neurological, or psychiatric disorder, or any malignancy treated within 1 year of Screening (with the exception of basal cell carcinoma of skin which is not advanced) that would prevent the individual from participating in the study due to risk to the scientific validity of study assessments or to personal well being

- 27. Any abnormal clinical chemistry, hematology, electrocardiogram (ECG), urinalysis, or physical finding at Screening that in the opinion of the Investigator is deemed clinically significant and that would prevent the individual from participating in the study due to risk to the scientific validity of study assessments or to the patient's personal well being
- 28. Hepatic dysfunction (history of cirrhosis with diagnosed portal hypertension, or alanine aminotransferase [ALT] or aspartate aminotransferase [AST] > 3 × upper limit of normal [ULN]) at Screening
- 29. Clinically significant renal insufficiency (ie, serum creatinine > 2.5 mg/dL or estimated glomerular filtration rate [eGFR] < 30 mL/min/1.73 m^2; calculated using the Chronic Kidney Disease Epidemiology Collaboration [CKD Epi] equation) at Screening
- 30. Impaired hemostasis (eg, thrombocytopenia [platelet count < 100,000/μL] at Screening; abnormal coagulation test defined as prothrombin time [PT] or partial thromboplastin time [PTT] > 1.5 × ULN, or international normalized ratio [INR] > 2 at Screening); past or present bleeding disorder, sickle cell or other platelet disorders, or carcinoid disorder)
- 31. Any surgeries or interventional procedures planned or anticipated during study participation
- 32. Positive urine test for amphetamines, barbiturates, benzodiazepines, cocaine, marijuana, methadone, methamphetamine, methylenedioxymethamphetamine, opiate, oxycodone, or phencyclidine. Exception is a test that is positive due to a prescription drug or medication.
- 33. Known history of alcohol or substance use disorder that is considered clinically significant per the judgement of the Investigator and that would represent risk to the scientific validity of study assessments or the patient's well being
- 34. Use of tobacco or nicotine-containing products (including but not limited to cigarettes, e-cigarettes, pipes, cigars, chewing tobacco, nicotine patches, nicotine lozenges, or nicotine gum) for at least 90 days prior to Screening
- 35. Previous participation in a study with temanogrel
- 36. Subjects who have received any investigational device or investigational drug within 30 days of Day 1, or 5 half-lives of the investigational drug (whichever is greater) prior to Screening
- 37. Hypersensitivity to temanogrel or placebo compounds
- 38. Inability to swallow capsules as required per the protocol
- 39. In the opinion of the Investigator, subject is not a candidate for blood sampling as required per the protocol

